## 2.7.4 Other safety data

### 2.7.4.1 Vital signs

Vital sign measurements include sitting systolic and diastolic blood pressures, sitting pulse, body temperature, height and body weight.

Three sitting measurements of blood pressure (SBP and DBP) and pulse may be taken for some vital sign assessment of some subjects. For post-baseline assessments, if 3 measurements are collected then the blood pressure and pulse values will be the average of the non-missing values of them. If more than one blood pressure/pulse assessment (scheduled or unscheduled) exists in a particular visit-window (as defined in [Section 2.1.2](#)), derivation should follow the rules as defined in [Section 2.1.2](#). Derivation of baselines for blood pressure and pulse are provided in [Section 2.1.1](#).

Height will be collected at screening visit only and will be summarized in demographics.

Analyses of vital sign measurements (excluding data collected on Day 1 protocol scheduled visit) using descriptive summary statistics (mean, median, standard deviation, min, max) for the change from baseline for each post-baseline visit-window will be performed. These descriptive summaries will be presented by vital sign parameter. Change from baseline will only be summarized for participants with both baseline and post-baseline values and will be calculated as:

$$\text{change from baseline} = \text{post-baseline value} - \text{baseline value}$$

The number and percentage of participants with clinically notable vital signs will be presented. Clinical notable vital signs values are defined in the table below.

**Table 2.9 Vital signs clinically notable values**

Vital Sign	Notable criteria
Pulse (beats/min, bpm)	>120 bpm Or <50 bpm
Systolic Blood Pressure (mmHg)	≥160 mmHg Or <90 mmHg
Diastolic Blood Pressure (mmHg)	≥100 mmHg Or <50 mmHg
Temperature (°C)	>38.3 °C (>101 °F)
Body weight (kg)	≥7% from baseline weight

All above summaries include only data up to and including safety cut-off.

### **2.7.5 Safety evaluation after last administration of study treatment**

The SAF will be used for analyses in this section.

Safety data collected after last administration of study treatment includes adverse events, vital signs, routine laboratory parameters, and laboratory assessments to measure total IgG, total IgM and B-cell repletion. No safety cutoff date will be applied in the analyses defined in this section. Safety data within the safety cutoff date but after last administration of study treatment will also be included. Only subjects who prematurely discontinue the study treatment will be included.

TEAEs beyond safety cutoff will be listed.

Spaghetti plots of time to B-cell repletion after study drug discontinuation will be presented with median value per timepoint overlaid.

In addition, subjects with notable lab abnormalities or clinically notable vital signs will be listed.

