9.3 Study completion and post-study treatment

Study completion is defined as when the last participant finishes their end of Post-treatment Follow-up visit and any repeat assessments associated with this visit have been documented and followed-up appropriately by the Investigator or, in the event of an early study termination decision, the date of that decision.

During the Post-treatment Follow-up period, the Investigator should consider the benefit/risk of initiation of alternative MS therapy in terms of the participant's clinical status, local regulations, treatment guidelines and local prescribing information. When initiating other immunosuppressive therapies with prolonged immune effects after study drug, the duration and mode of action should be taken into account because of potential additive immunosuppressive effect.

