#### Treatment (12 months):

During the Treatment period, all eligible participants will receive initial dosing with ofatumumab 20 mg s.c. injection at Baseline/Week 0 (BL/W0), W1 and W2, followed by subsequent monthly dosing starting at W4 (Month 1/M1; a study month is defined as 28 days). The first s.c. injection at W0 will be administered

All participants will have an End of Study (EOS) visit at the end of the Treatment period, when a participant has reached the maximum of 12-month treatment, or at the time a participant prematurely discontinues study treatment. After study treatment discontinuation, participants may initiate alternative MS therapy according to local standard of care if clinically indicated (refer to [\[Protocol Section 9.3\]](#)).

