### 2.1.2.2 Visit windows after study drug discontinuation

For summaries of data collected after study drug discontinuation, data from both Treatment period and Post-treatment Follow-up period will be considered. All reporting will be done based on visit windows defined relative to the last administration of study drug.

The visit window definitions are provided in [Table 2-8](#) where the Start day and End day are relative to the date of last administration of study drug. For the “Last assessment on drug”, the last assessment with non-missing value taken before or on the date of last administration of study drug will be summarized (no visit window applies). For the “Month 3 after LDD (last dose date)” visit-window, assessments taken at least 1 day after but no more than 126 days after the date of last administration of study drug will be considered. LDD stands for last dose date and will be footnoted in applicable output(s).

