## **2.7      Safety analyses**

All safety analyses will be conducted using the SAF. The safety cutoff is defined as 100 days after the last dose administration of study drug (or EOS for participants continue with commercial ofatumumab immediately after EOS, or min(last dose of study medication + 100 days, date of switching to another DMT - 1) for participants who have such switch in the Post-treatment Follow-up period). Unless explicitly otherwise stated, only data up to and including the safety cut-off will be included in the analysis and data beyond this time point for a given subject will be excluded from the safety analysis.

The assessment of safety will be primarily based on the frequency of adverse events (including death and non-fatal serious adverse events). Additional safety assessments include laboratory tests and vital sign measures. Clinically significant findings in these additional safety assessments and other will be reported as adverse events and analyzed as such.

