### 2.7.3.1 Other special lab results

Non-routine laboratory data include pregnancy test results, B-cell counts, total IgG and total IgM. All data will be listed appropriately.

The B-cell counts, total IgG and total IgM will be summarized using descriptive statistics by visit-window.

In addition, number and percentage of participants with B-cells < the lower limit of normal (LLN) value (i.e. B-cell depleted) will be presented by visit-window. All B-cell summaries defined in this section will include data up to last dose date + 30.

Number and percentage of participants meeting the notable low level criteria in IgG or IgM at least once will be provided. A notably low IgG level is defined as a level that is 20% below the LLN and a notably low IgM level is defined as a level 10% below the LLN.

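### SAP 2.7.5 drops the DMT-switch limit along with the 100-day limit, so B-cell values taken under another DMT can enter the repletion plot and its median

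*SAP*

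**What the plan says.** SAP 2.1.1 (general definitions) and SAP 2.7 define the safety cut-off as 100 days after the last dose. For participants who change therapy in follow-up, it is the earlier of that date and the day before the change: "date of switching to another DMT - 1) for participants who have such switch in the Post-treatment Follow-up period".

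SAP 2.7.5 covers safety after the last administration. It restricts the population ("Only subjects who prematurely discontinue the study treatment will be included") and removes the cut-off ("No safety cutoff date will be applied in the analyses defined in this section"). The B-cell output is specified in one sentence: "Spaghetti plots of time to B-cell repletion after study drug discontinuation will be presented with median value per timepoint overlaid".

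The same documents foresee new MS therapy in these participants. SAP 1.1 says that after study treatment is discontinued "participants may initiate alternative MS therapy according to local standard of care if clinically indicated". Protocol 9.3 adds: "During the Post-treatment Follow-up period, the Investigator should consider the benefit/risk of initiation of alternative MS therapy". Protocol Table 8-2 schedules B-cell samples at EOS+3 and EOS+6 months and records newly started MS treatment.

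**The concern.** The waiver treats the cut-off as one rule, but it does two jobs. The 100-day part limits how long after ofatumumab an observation counts, and it has to go if repletion is to be seen. The switch part limits observations to time without another DMT. Without it, a B-cell count can reflect the next drug rather than recovery from this one.

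The plot is labelled as repletion after study drug discontinuation, and its median is the single line that most readers will take away. Where the next drug lowers B cells, the error goes in one direction: recovery after ofatumumab appears slower. The plotted group is small, so a few participants can move the median. What is at stake is how repletion time is read in the study report, not the primary result.

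**Working it through.** **Step 1. Is the switch limit restored anywhere else?** Four places could do so.

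- *SAP 2.1.1 and 2.7.* The switch limit sits inside the definition of the safety cut-off. SAP 2.7.5 waives that cut-off without keeping any part of it.
- *SAP 2.1.2.2 and Table 2-8.* For post-discontinuation data, "All reporting will be done based on visit windows defined relative to the last administration of study drug". The windows run to Month 15 after the last dose and contain no rule on other DMTs.
- *SAP 2.7.3.1.* "All B-cell summaries defined in this section will include data up to last dose date + 30". By its own words this covers only the summaries in 2.7.3.1, and a 30-day limit could not govern a repletion plot.
- *SAP 2.1.1, on-treatment period.* It ends 30 days after the last injection and so cannot govern a plot of later data.

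Nothing in the visible text censors, flags or separates B-cell values after a switch. The blacked-out SAP section was not relied on.

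**Step 2. Can a post-switch value occur?** Yes. Other MS therapy is allowed after discontinuation, and samples follow at EOS+3 and EOS+6 months. The list in Protocol 6.2.2 applies only while study treatment is being taken.

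**Step 3. How many participants are plotted?** The plan gives no figure. Inputs are from Protocol 12.8 and SAP 3.1: 85 completers, 15% planned dropout, and 10.3% and 17.3% dropout in the two pivotal trials.

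- Planned size reproduced: 85 / (1 − 0.15) = 100.
- Plotted: 100 × 0.15 = 15, with a range of 100 × 0.103 = 10.3 to 100 × 0.173 = 17.3, so about 10 to 17.

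This takes dropout as a stand-in for premature treatment discontinuation.

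**Step 4. How far could the median move?** Let n be the number plotted and s the number who have switched to a B-cell-lowering DMT by a given timepoint. Assume that all n give a sample and that switchers hold the s lowest values. The overall median has rank (n + 1)/2, which is rank (n + 1)/2 − s among the n − s unswitched. Its percentile among the unswitched, taken as (rank − 0.5)/number, is (n/2 − s)/(n − s).

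| s | n = 10 | n = 15 | n = 17 |
|---|---|---|---|
| 0 | 5/10 = 50% | 7.5/15 = 50% | 8.5/17 = 50% |
| 1 | 4/9 = 44% | 6.5/14 = 46% | 7.5/16 = 47% |
| 2 | 3/8 = 38% | 5.5/13 = 42% | 6.5/15 = 43% |
| 5 | 0/5: below every unswitched value | 2.5/10 = 25% | 3.5/12 = 29% |

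With n = 15 and 8 or more switchers, the median (rank 8) is itself a post-switch value. The documents give no value for s, so the table shows sensitivity and is not a forecast.

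**The case against.** The strongest case against the point is that the distortion is conditional and may not occur. It needs a plotted participant to start a DMT that lowers B cells before a follow-up sample. Protocol 1.1 lists six DMTs approved in China as of May 2021: two interferons, teriflunomide, fingolimod, siponimod and dimethyl fumarate. None is an anti-CD20 antibody, and the documents do not say how any of them affects B-cell counts. The same section says that ocrelizumab was not approved there. Protocol 9.3 also asks investigators to weigh additive immunosuppression before starting therapies with prolonged immune effects. All of this stands. A reader might infer that the bias is certain or systematic, and the documents do not support that.

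The assumptions in Step 4 are also unfavourable. Some discontinuers will leave the study and give no sample, and some unswitched participants may still be depleted and rank no higher than switchers. With one or two switchers among 15, the shift is modest.

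Stopping the data at a switch is not neutral either. Late medians would then describe only those who had not switched, a self-selected part of an already small group. Using all off-drug data is a defensible choice for a general safety section. This bears on the form of the remedy: showing post-switch values distinctly loses nothing, and restricting only the median answers most of the selection objection, provided that n is printed.

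Finally, repletion is not a listed endpoint, the study tests no hypothesis, and the individual curves stay visible. That limits the consequence, but it does not supply the missing rule.

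**Conclusion.** The point holds as a gap in a data rule. By waiving the whole safety cut-off, SAP 2.7.5 admits B-cell values taken under another DMT into a plot and median labelled as repletion after ofatumumab. If that DMT lowers B cells, repletion can look slower than it is. The size is unknown. With 15 plotted and the assumptions of Step 4, the median falls at about the 50th, 46th, 42nd or 25th percentile of the unswitched for 0, 1, 2 or 5 switchers. A DMT without a B-cell effect would cause no distortion.

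Three further readings are tempting, but the documents do not support them.

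- *The study relies on this plot in follow-up.* Protocol 3 and SAP 1.1 only let an investigator follow an individual outside the study, for example if that person's B cells have not recovered. Nothing depends on the plot or its median.
- *IgG and IgM are affected in the same way.* SAP 2.7.5 names them among the data collected, but specifies a plot and median for B cells only.
- *The data must also stop at commercial ofatumumab.* The documents describe that route for completers, and SAP 2.7.5 already excludes completers.

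The annualized relapse rate is not affected.

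**What to change.** In SAP 2.7.5, keep the waiver of the 100-day limit and add a sentence to this effect: the overlaid B-cell median uses only values obtained before the start of any other DMT; values from that date on are shown in a distinct line style, or in the listing only; and the number of participants contributing to the median is printed at each timepoint.

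The cost is one sentence and a date filter. New MS treatment is already recorded in follow-up (Protocol Table 8-2), and the SAP already uses a switch date in its safety cut-off. The downside is that late medians rest on fewer values and describe only participants who have not switched. The printed n and a footnote should say so.

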12.3 Treatments

The summary of exposure and time-at-risk will be based on the SAF.

Exposure to investigational study medication is defined as the number of days spent on study treatment divided by 365.25 days. Intermediate treatment interruptions will be subtracted from drug exposure. Exposure to investigational study medication will be summarized with number and percentage of participants by time category, and with summary statistics of the number of participant years of exposure. Further details will be included in the statistical analysis plan (SAP).

Time-at-risk is defined as the number of days spent in the study, from first dose to the last dose of study medication, plus the safety data cut-off of 100 days (or until EOS for participants continue with commercial ofatumumab immediately after EOS, or until last dose of study

medication plus 100 days or one day before switching to another DMT, whichever comes earlier, for participants who have such switch in the PT FU). Intermediate treatment interruptions will be included in time-at-risk calculations. Time-at-risk corresponds to the time window used for adverse event reporting and can serve as a denominator to safety (e.g. in exposure-adjusted incidence rates). Time-at-risk will be summarized in a similar way to exposure to investigational study medication. Further details will be specified in the SAP.

Concomitant medications and significant non-drug therapies prior to and after the start of the study treatment will be summarized and/or listed according to the Anatomical Therapeutic Chemical (ATC) classification system.

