12.5.2 Safety endpoints

For all safety analyses, the safety set will be used. Unless explicitly stated otherwise, only data up to and including the safety cut-off of 100 days after permanent study treatment discontinuation or treatment completion (or EOS for participants continue with commercial ofatumumab immediately after EOS, or min(last dose of study medication + 100 days, date of switching to another DMT - 1) for participants who have such switch in the PT FU) will be

included in the analysis and data beyond this time point for a participant will be excluded from safety analysis.

The assessment of safety data will be primarily based on the frequency and percentage of adverse events (including death and non-fatal serious adverse events). Additional safety assessments such as laboratory tests, physical examination (including examination of skin), and vital signs will be analyzed. Clinically significant findings in these additional safety assessments will be reported as adverse events and analyzed as such. The detailed analyses of additional safety assessments will be defined in the SAP.

Adverse events

Treatment-emergent adverse events including serious adverse events and deaths will be summarized up to and including the safety cut-off.

The number (and percentage) of participants with treatment emergent adverse events (events started after the first dose of study medication or events present prior to start of treatment but increased in severity based on preferred term) will be summarized in the following ways:

- by primary system organ class and preferred term.
- by primary system organ class, preferred term and maximum severity.

Separate summaries will be provided for adverse events related to study treatment, death, serious adverse events, and other significant adverse events leading to interruption or discontinuation, if appropriate.

Specific risks of interest will be defined by combinations of adverse event and/or other relevant safety data (e.g. lab data). The number (and proportion) of participants fulfilling such risk definitions will be summarized.

A participant with multiple adverse events within a primary system organ class will only be counted once towards the total of the primary system organ class.

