**Table 2-8 Visit-windows after study drug discontinuation**

Visit-window	Start day	Target Day	End day
Last assessment on drug	NA	NA	NA (see above or Section 2.1.1 )
Month 3 after LDD	2	84	126
Month 6 after LDD	127	168	210
Month 9 after LDD	211	252	294
Month 12 after LDD	295	336	378
Month 15 after LDD	379	420	462

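### SAP 2.7.5 leaves followed-up completers out of the post-treatment B-cell repletion plot; separately, SAP Section 4 does not declare that the exposure-adjusted rates were dropped

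*SAP*

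**What the plan says.** **Who is followed.** Under Protocol Section 3 and Table 8-2, everyone except completers who move to commercial ofatumumab attends visits at EOS+3 and EOS+6 months. B-cells, IgG and IgM, haematology, chemistry and vital signs are scheduled at both.

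**Cut-offs.** SAP 2.7: "The safety cutoff is defined as 100 days after the last dose administration of study drug". It comes earlier for commercial continuers (EOS) and for those who switch DMT (the day before the switch). For B-cells, SAP 2.7.3.1 is tighter: "All B-cell summaries defined in this section will include data up to last dose date + 30". The default exclusion originates in Protocol 12.5.2: "data beyond this time point for a participant will be excluded from safety analysis".

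**After the last dose.** SAP 2.7.5 applies no safety cut-off, but then states: "Only subjects who prematurely discontinue the study treatment will be included". Its one output other than a listing is: "Spaghetti plots of time to B-cell repletion after study drug discontinuation will be presented with median value per timepoint overlaid". SAP Table 2-8 ("Visit-windows after study drug discontinuation") supplies windows counted from the last administration.

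**Where the 100 days start.** The SAP counts from last dose. So does time at risk in Protocol 12.3, which runs "from first dose to the last dose of study medication, plus the safety data cut-off of 100 days". Protocol 12.5.2 instead sets a "safety cut-off of 100 days after permanent study treatment discontinuation or treatment completion".

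**Exposure-adjusted rates.** Protocol 12.5.2 specifies them for all TEAEs and for serious TEAEs, because follow-up length varies. The SAP Document History records their removal in Amendment 1. SAP Section 4, which is meant to list departures from the protocol's analyses, says that none apply, and SAP Section 1 states that the SAP agrees with the protocol.

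**The concern.** Both documents give incomplete B-cell recovery at the end of follow-up as an example of why an investigator might keep following someone. Completers have had the full 12-month regimen and are sampled at both follow-up visits, yet SAP 2.7.5 keeps them out of the only display of repletion. The plotted medians would describe people who stopped early, and would invite reading as repletion after ofatumumab in general.

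The second matter is independent of the first. A reader who relies on SAP Section 4 would conclude that every analysis in the protocol was kept. That is not so.

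**Working it through.** **Calendar.** A study month is 28 days (Protocol Section 3). The schedule reproduces: M3 = 3×28 = 84, M6 = 168, M9 = 252, M12/EOS = 12×28 = 336, all as in Protocol Table 8-1. No dose is given at M12/EOS, so the last scheduled dose is at M11: 11×28 = Day 308. The SAP cut-offs for an on-schedule completer are then 308+30 = Day 338 (B-cells) and 308+100 = Day 408 (other safety data).

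| Visit | Day | After last dose | B-cell cut-off (338) | General cut-off (408) | Table 2-8 window |
|---|---|---|---|---|---|
| EOS | 336 | +28 | inside | inside | 2–126 |
| V1 | 336+84 = 420 | +112 | 82 days past | 12 days past | 2–126 |
| End of FU | 336+168 = 504 | +196 | 166 days past | 96 days past | 127–210 |

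**Sensitivity.** Follow-up months of 30 days give +118 and +208; calendar months give about +119 and +211; a last dose 7 days late gives +105 and +189. Both visits stay outside both cut-offs each time.

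**Starting point of the 100 days.** If treatment completion in Protocol 12.5.2 means EOS, the cut-off is 336+100 = Day 436. V1 is then inside by 436−420 = 16 days, and End of FU is outside by 504−436 = 68 days. The two wordings could therefore decide whether completers' V1 laboratory, vital-sign and IgG/IgM values are summarised. B-cells are unaffected, because their limit is +30.

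**Two visits in one window.** A completer's EOS (+28) and V1 (+112) both fall in 2–126. SAP 2.1.2.3 gives a selection rule only for several unscheduled visits. By distance from target day 84, |84−28| = 56 and |84−112| = 28, so the closest-to-target rule picks V1. The same clash can arise for an early stopper.

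**Reach (illustration only).** The documents do not say how many completers enter follow-up. Take the planned 15% dropout (Protocol 12.8.1), so 85 completers and 15 dropouts per 100. Let f be the share of completers and g the share of dropouts who are followed; both are assumptions. The plot omits 85f/(85f+15g) of those followed.

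- With g = 1: 0% at f = 0; 8.5/23.5 = 36% at f = 10%; 21.25/36.25 = 59% at f = 25%; 42.5/57.5 = 74% at f = 50%.
- With g = 0.5: 0% at f = 0; 8.5/16 = 53%, 21.25/28.75 = 74% and 42.5/50 = 85% at the same later values of f.
- With g = 1, more than half is omitted once f exceeds 15/85 = 17.6% (10.3/89.7 = 11.5% and 17.3/82.7 = 20.9% at the two pivotal dropout rates). A smaller g lowers that threshold.

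**Rates.** Without a switch of therapy, a completer's serious-TEAE window is 336 days if continuing commercially and 504 if followed: 504/336 = 1.50. For other TEAEs it is 336 against at most 408: 408/336 = 1.21; a switch to another DMT shortens the 408. SAP 2.4.1 still defines and summarises time at risk, but states no end of SAE time at risk for commercial continuers.

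**The case against.** The case for leaving (a) alone is substantial.

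- *No commitment is broken.* No visible endpoint concerns B-cell repletion, Protocol Section 12 allows summaries or listings, and SAP 2.7.3.1 lists all B-cell and immunoglobulin data. The protocol glossary defines treatment discontinuation as stopping before planned completion, so the plot's population matches its title. This stands. A reader might infer a breach of the protocol; the documents do not support that.
- *Few people may be affected.* Protocol 6.1.4 expects ofatumumab to be commercially available when the first participant completes. This stands too. A reader might infer that the plot omits most of those followed; that depends on f and g, which the documents do not give.
- *Completers' safety data are not confined to listings.* Correct. TEAEs up to the cut-off are tabulated, and serious TEAEs and deaths are summarised whatever the cut-off. The gap concerns follow-up B-cell, IgG/IgM, laboratory and vital-sign values. SAP 2.7.5 specifies no IgG/IgM, laboratory or vital-sign summary for early stoppers either.
- *Adding completers may mix repletion with the effect of a new therapy.* SAP 2.7.5 lifts the DMT-switch limit along with the 100 days. This is a fair point about the remedy, and it applies to early stoppers already in the plot.
- *Redacted text could hold the analysis.* Not excluded, but unlikely: SAP 2.1.2.1 ties the hidden 2.12.1 to disability progression, and SAP 2.11 sends B-cell and immunoglobulin summaries to 2.7.3.1.

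On (b), the removal is disclosed in the Document History, so concealment should not be inferred. With one arm there is no between-arm contrast to bias. Section 4 is still wrong as written.

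**Conclusion.** (a) Holds as a gap in reporting worth closing. On the 28-day schedule and with the SAP's last-dose anchor, both follow-up B-cell samples of every followed completer fall outside the plot and every summary, by 82 and 166 days against the B-cell limit. Their other laboratory, immunoglobulin and vital-sign values miss the general cut-off by 12 and 96 days. The repletion medians are therefore selective. The timing result does not depend on how a month is counted. The 12-day exclusion of V1 does depend on the anchor and reverses if the 100 days run from EOS. The number of people affected is unknown and may be small.

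(b) Separate and minor, but a plain conflict between the current protocol and the current SAP: a specified output is missing and Section 4 is inaccurate. The primary and MRI endpoints are untouched by either part.

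**What to change.** (a) In SAP 2.7.5:

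- Replace the restriction with: *subjects who prematurely discontinue study treatment and completers who enter the Post-treatment Follow-up period, shown separately*. Apply it to the B-cell repletion plot, and add descriptive B-cell and IgG/IgM summaries by the existing Table 2-8 windows.
- When two scheduled visits share a window, use the one closest to the target day.
- In both groups, flag or censor values from the date of switching to another DMT, as the SAP safety cut-off already does.
- Word the start of the 100 days identically in Protocol 12.3, Protocol 12.5.2 and the SAP, and say whether completers' V1 is in or out.

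(b) Reinstate the exposure-adjusted rates for TEAEs and serious TEAEs using the time at risk in SAP 2.4.1, ending SAE time at risk at EOS for commercial continuers, in line with Protocol 10.1.3. Otherwise, correct Section 4 to declare and justify the removal, and amend the consistency statement in Section 1.

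The cost is some SAP wording, one plot panel and a few descriptive tables, plus either two rate tables or a corrected Section 4 and Section 1. The anchor also needs a wording change in the protocol. No new data are needed. If few completers are followed, their medians will be imprecise and should be shown with the number contributing.
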